9.7 Analysis of the secondary efficacy variables

9.7.1 Analysis of change from baseline in FSIQ-RMS weekly symptoms score (Fatigue) to Week 108

9.7.1.1 Hypothesis and statistical model

Change from baseline in FSIQ-RMS weekly score is analyzed using a repeated measurements ANOVA model to compare the change from baseline to Week 108 across both treatment groups. The underlying hypotheses are expressed as two means, assuming the endpoint follows a normal distribution:

$$H_{0, \text{FSIQ}}: \mu_{\text{P20mg, W108}} - \mu_{\text{T14mg, W108}} = 0 \text{ vs.}$$

$$H_{1, \text{FSIQ}}: \mu_{\text{P20mg, W108}} - \mu_{\text{T14mg, W108}} \neq 0.$$

The hypotheses are assessed at a statistical significance level of $1/3 \alpha = 0.05/3$ as per the overall testing strategy [see Section 9.1.1] based on a t-test for contrasts of mean estimates, once the null hypothesis for the primary endpoint has been rejected.

9.7.1.2 Statistical Analysis

The main analysis will be based on the FAS. A mixed effect model repeated measures (MMRM) which includes baseline (FSIQ-RMS SWS_{c Base}) and the two stratification factors, i.e., prior use of DMT (Yes/No), baseline EDSS category (EDSS ≤ 3.5, EDSS > 3.5) as covariates, treatment (fixed effects), visit, treatment by visit interaction, and baseline (FSIQ-RMS SWS_{c Base}) by visit interaction is applied. An unstructured co-variance structure shared across treatment groups will be used to model within patient errors. The Kenwood Roger approximation will be used to estimate denominator degree of freedom and adjusted standard errors. This model assumes that missing data follow the

missing at random assumption. Subjects with at least one available score at a post-baseline visit and at the baseline visit are included in the analysis.

Treatment effects per visit are derived based on (difference in) least-square means with corresponding 95% CIs and p-values derived using the t-distribution. They will be presented in tabular and graphical form.

The main comparison for this secondary endpoint is conducted on the difference in least-square means at Week 108. The corresponding p-value is compared to the local significance level of $1/3 \alpha = 0.05/3$.

The SAS code for this model is as follows (considered “draft” until fully validated at analysis stage):

```
proc mixed data=;  
  class subject treatment visit DMT EDSS;  
  model Chg = Base DMT EDSS treatment visit treatment*visit Base*visit/ noint  
  ddfm=kr;  
  repeated visit / sub = subject type = un;  
  lsmeans Treatment*Visit / pdiff CL OM;  
run;
```

If the normality assumptions seems grossly violated the analysis will be conducted based on a rank ANCOVA of change from baseline to Week 108 using a stratified test [see Section 10.3.3].

9.7.1.3 Supportive / Sensitivity analyses

Further supportive and sensitivity analyses will be carried out as indicated below. Results in terms of treatment difference (95% CI) at Week 108 will be tabulated and forest plots will be provided.

9.7.1.3.1 Change from baseline in FSIQ-RMS weekly symptom score to Week 108 - delta worsening adjustment in ponesimod

To evaluate the robustness of the main analysis to deviations from the missing at random assumption a delta worsening multiple imputation analysis is conducted. Starting with a MAR multiple imputation approach the mean effect following drop-out (last score available) is assumed to worsen in the ponesimod 20 mg arm by delta, δ_P , using a marginal approach. δ_P is increased by small increments until the outcome of the analysis shifts from significance to non-significance. An increment size of 0.5 is applied (clinical meaningful threshold for change / 10). For the teriflunomide 14 mg arm a MAR multiple imputation is performed, i.e., without adding any worsening ($\delta_T = 0$ for all analyses). Analysis for the imputed datasets follows the main analysis and a pooled treatment difference estimate, 95% CI and p-value are obtained for each delta. Results are displayed graphically versus delta.

The analysis is only conducted if the main analysis is significant.

Non-monotone missing data (in-between missing data points) are imputed based on MCMC methods using Proc MI in SAS in a first step of the multiple imputation procedure. The covariates baseline FSIQ score, prior use of DMT, and baseline EDSS category are considered in the imputation model.

9.7.1.3.2 Change from baseline in FSIQ-RMS weekly symptom score to Week 108 (LOCF) - ANCOVA

An ANCOVA of change from baseline to Week 108 based on LOCF is conducted, adjusting for the same covariates as in the main analysis (baseline value and stratification variables). Mean, mean difference and 95% CIs are presented.

9.7.1.3.3 Change from baseline in FSIQ-RMS weekly symptom score to Week 108 - based on on-treatment data (up to EOT + 7 days)

The above MMRM for the main analysis will be repeated fitting the model only to data collected up to EOT + 7 days. A treatment comparison at Week 108 is conducted.

9.7.1.3.4 Change from baseline in FSIQ-RMS weekly symptom score to Week 108 - Per protocol analysis

A per-protocol analysis will be conducted as supportive. This analysis will be based on subjects in the PPS and will only include data in the analysis that were collected prior to a protocol deviation leading to exclusion from the per protocol analysis. A model as for the primary analysis is applied on the reduced data and a treatment comparison at Week 108 is conducted.

9.7.1.4 Descriptive analyses

Daily responses to FSIQ-RMS symptoms items 1, 2, 3, 4, 5, 6, and 7, FSIQ-RMS Symptoms Daily Scores will be listed, as well as the FSIQ-RMS weekly symptoms score. For each treatment group, by visit, Symptoms Weekly Scores based on observed data and LOCF, and change from baseline of these scores will be summarized using descriptive statistics. Change from baseline by visit is in addition presented graphically using mean (\pm SE). A separate by visit summary displaying only change from baseline up to EOT + 7 days will be provided.

Frequency and percentages of subjects with an available score will be summarized by visit.

9.7.1.5 Subgroup analyses

Subgroup analyses for change from baseline to Week 108 in FSIQ-RMS symptoms score will be conducted on the subgroup variables listed in Section 8, apart from recruitment period, using the FAS. The analysis is conducted to assess consistency of the overall treatment effect across subgroup variables.

The above main MMRM analysis will be repeated within subgroup levels using a model as for the main analysis without adjustments for stratification factors. Estimates of mean at Week 108 by treatment arm, difference in means with 95% CIs within each subgroup level will be presented, accompanied by the number of subjects per category.

The treatment-by-subgroup interaction p-value is estimated for each subgroup variable from a separate model including treatment, the subgroup and the treatment-by-subgroup interaction term(s). Interactions with a p-value < 0.01 will be investigated further to determine the nature of the interaction (quantitative or qualitative) and the association with other subgroups.

Results are presented in a summary table and in a forest plot. The forest plot will include the 'overall' treatment effect, based on the main efficacy analysis as a reference line. Point estimates are presented within the forest plot with its size proportional to the number of subjects in the subgroup.

9.7.2 Analysis of cumulative unique active lesions from baseline up to Week 108 (CUAL)

9.7.2.1 Hypothesis and statistical model

A generalized linear model with negative binomial distribution as described in Section 10.1 will be assumed for the number of cumulative unique active lesions from baseline to Week 108.

Two-sided hypotheses are expressed in terms of the model parameters μ_{P20mg} and μ_{T14mg} from the negative binomial regression model. The null hypothesis is that the CUAL (μ) does not differ between ponesimod 20 mg and teriflunomide 14 mg. The alternative hypothesis is that the CUAL differs between ponesimod 20 mg and teriflunomide 14 mg.

$$H_{0, CUAL}: \mu_{P20mg} - \mu_{T14mg} = 0$$

vs

$$H_{1, CUAL}: \mu_{P20mg} - \mu_{T14mg} \neq 0$$

The treatment effect will be evaluated based on the relative reduction in mean CUAL for ponesimod 20 mg compared to teriflunomide 14 mg, with corresponding 95% Wald CI. The null hypothesis will be tested by a two-sided Wald test, comparing the p-value to the local significance level as per the overall testing strategy [see Section 9.1].

9.7.2.2 Statistical analysis

The main analysis of the secondary endpoint CUAL will be performed on the FAS using a negative binomial regression model with treatment as a factor and the binary stratification variables (EDSS \leq 3.5 versus EDSS > 3.5; DMT within last 2 years prior to randomization [Yes/No]) and Gd+ T1 lesions at baseline (absent or present) included in

the model. The model also includes an offset variable defined as the log of the time up to last MRI (in years) considered for analysis.

Mean model-based estimates of the number of CUALs per year will be provided by treatment group, as well as 95% Wald CIs. A rate ratio comparing ponesimod 20 mg with teriflunomide 14 mg will be derived from the model including 95% Wald CIs and the corresponding p-value. The dispersion parameter will also be displayed.

The fit of the model will be assessed and other distributions such as the Poisson distribution will be considered in case of a lack of fit.

Descriptive summary statistics of the number of CUALs up to Week 108 continuous and in categories (0, 1–5, 6–10, 11+) will be presented. The total number of CUALs as well as the total cumulative time up to the last MRI scan (summed for all subjects) will also be displayed. From the total number of CUALs and the total cumulative time up to the last MRI scan the raw number of CUALs per year will be calculated and summarized.

A listing of CUAL data will be presented.

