2 STUDY DESIGN AND FLOW

The study is a prospective, multicenter, randomized, double-blind, active-controlled, parallel-group, Phase 3, superiority study in adult subjects with relapsing forms of MS. 1133 subjects are randomized in two groups: ponesimod 20 mg or teriflunomide 14 mg, using a 1:1 ratio, stratified by use of multiple sclerosis (MS) disease-modifying treatment in the last two years prior to randomization (yes, no) and by baseline Expanded Disability Status Scale (EDSS) score ($EDSS \leq 3.5$, $EDSS > 3.5$).

The study is conducted at approximately 161 sites (randomized subjects) in 28 countries in North America, Eastern and Western Europe, and Pacific region.

[figure not shown]

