- **Time since most recent relapse (months) at screening**, defined as [Date of screening – Onset date of latest MS relapse prior to screening + 1] in days / 30.4375. From eCRF form ‘MS History - Relapse’ at screening. Take the most recent “Onset date of previous relapse” among all previous relapses entered on the ‘MS History - Relapse’ eCRF. Partial onset dates are imputed to the maximum of [Date of first MS symptoms, 1st day of the month] (if the day is missing) and to the maximum of [Date of first MS symptoms, 1st of January] (if the day and month are missing). Data collected at re-screening overwrites the initially entered data.

- **Number of relapses in the year prior to study entry**, as reported in the corresponding question on the ‘MS History - Relapse’ eCRF (i.e., not based on recorded onset dates of previous relapses). Data collected at re-screening overwrites the initially entered data.
 - **Number of relapses in the 2 years prior to study entry** as reported in the corresponding question on the ‘MS History - Relapse’ eCRF (i.e., not based on recorded onset dates of previous relapses). Data collected at re-screening overwrites the initially entered data.
 - **Presence of Gd+ T1 lesions (yes/no)** on baseline MRI scan as provided by the MRI central reading.
 - **Number of documented Gd+ T1 lesions** on baseline MRI scan as provided by the MRI central reading.
 - **Volume of T2 lesions** on baseline MRI scan as provided by the MRI central reading.
 - **Number of T2 lesions** on baseline MRI scan as provided by the MRI central reading, categorized into < 9 and ≥ 9 .
 - **Highly active disease (yes, no)**. A subject is considered to have highly active disease if one or both of the following conditions are met:
 - Any disease modifying therapy for MS as specified in Section 5.2.5.4 received during the year* before randomization and one or both of the following conditions are met:
 - ≥ 1 relapse within 1 year prior to study entry and the baseline MRI read centrally shows either ≥ 1 Gd+ T1 lesion and/or ≥ 9 T2 lesions
 - Number of relapses within 1 year prior to study entry \geq number of relapses between 2 and 1 year prior to study entry, for subjects with at least one relapse within 2 years prior to study entry.
 - ≥ 2 relapses within the 1 year prior to study entry and baseline EDSS score > 2 and baseline MRI read centrally shows ≥ 1 Gd+ T1 lesion.

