5.4.2.1.1 Variables for supplementary analysis

For supplementary analyses change from baseline for the following weekly scores will be considered in addition separately:

- **Up to EOT + 7 days**
- **Per protocol** - for subjects in the PPS data up to the first protocol deviation leading to exclusion from the per protocol analysis

- **LOCF by visit** weekly scores by visit based on last observation carried forward (LOCF) will be derived. Baseline data will not be carried forward.

5.4.2.2 Cumulative number of combined unique active lesions (CUAL) from baseline to Week 108

CUAL from baseline to Week 108 is calculated as the sum of new T1 Gadolinium-enhanced (Gd+) lesions and new or enlarging T2 lesions without Gd enhancement on T1 at all post-baseline MRI visits up to the Week 108 MRI visit (if the Week 108 visit is missing, consider all post-baseline scans up to EOS).

MRI scans are scheduled at Baseline, at the Week 60 Visit, and the Week 108 Visit. For subjects who prematurely discontinue treatment, an additional premature EOT visit MRI is scheduled. Unscheduled MRI scans may be conducted in addition.

MRI data are read centrally and provided to the sponsor.

To account for varying observation time, e.g. in case of premature study withdrawal or missing MRI assessments, the analysis will be adjusted by: $\text{Time up to the last MRI (years)} = (\text{Date of last MRI considered in derivation of CUAL} - \text{Randomization date} + 1) / 365.25 \text{ days}$.

Rationale: Due to the fact that yearly MRI scans are scheduled, the CUAL count is expected to be mainly driven by new T2 lesions. The number of T2 lesions is expected to increase with observation time. In contrast, in studies where MRI scans are scheduled more regularly, the CUAL count is mainly driven by new T1 Gd+ lesions which are expected to increase with the ‘Number of MRI scans’ conducted. Also, in this study, there is an additional MRI following premature treatment discontinuation which can occur at any time, therefore the ‘number of MRI scans’ is not necessarily expected to be a good approximation of the observation time.

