9.7.2.3 Supportive/sensitivity analyses

9.7.2.3.1 Analysis of CUALs from baseline to EOS - Missing data sensitivity: Imputation from last MRI scan to Week 108

To assess the impact of missing data on CUAL, i.e., last MRI scan conducted prior to Week 108, sensitivity analyses will be performed. These include the imputation of CUALs between last MRI scan and the theoretical Week 108 using different assumptions for the period with missing data on the FAS.

Time up to the last MRI scan is presented with a cumulative distribution function by treatment arm.

Sensitivity analyses for the main analysis will be conducted based on the MI method for negative binomial count data [see Section 10.1.1].

For subjects with missing Week 108 MRI scan the number of CUALs from last MRI scan up to the theoretical Week 108 will be imputed under different assumptions.

For all MI methods, subjects without a post-baseline MRI scan will be imputed based on baseline covariates; they will not be excluded from the analyses. No imputation is performed for subjects with missing baseline MRI; they are excluded from the analyses.

Imputation of events is conducted under the following assumptions: Missing at Random (MAR), Copy reference, Jump to reference. The corresponding interpretations are detailed in Section 9.6.4.3, only that imputation is now conducted post last MRI scan instead of post study-withdrawal.

For each imputed dataset the analysis is adjusted for the same covariates as for the main analysis, i.e., the binary stratification variables (EDSS \leq 3.5 versus EDSS $>$ 3.5; DMT within last 2 years prior to randomization [Yes/No]) and Gd+ T1 lesions at baseline (absent or present).

The rate ratio estimates with corresponding 95% CIs will be computed for each method.

9.7.2.3.2 *Analysis of CUAL - per protocol analysis*

The main analysis will be repeated using a per protocol analysis approach, i.e., on the PPS and considering MRI scans up to the first deviation leading to exclusion from the per protocol analysis. The number of CUALs (per protocol) is used as a response variable and the log of the time to the last MRI scan (years) considered in the per-protocol analysis as an offset variable [see Section 5.4.2.2]. Covariate adjustment as for the main analysis will be applied.

9.7.2.3.3 *Analysis of CUALs from baseline to EOT + 7 days*

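### In the alpha-controlled CUAL model the only MRI covariate is Gd+ absent/present; adding the collected Gd+ lesion count and T2 volume could gain precision at little cost

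*SAP*

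**What the plan says.** SAP 9.7.2.2 fits a negative binomial regression to CUAL on the FAS. Besides treatment, the covariates are the EDSS stratum, the DMT stratum and "Gd+ T1 lesions at baseline (absent or present"). Follow-up enters through "an offset variable defined as the log of the time up to last MRI (in years) considered for analysis".

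SAP 5.2.2 lists further baseline values from the central MRI reading, among them "Number of documented Gd+ T1 lesions" and "Volume of T2 lesions". Neither is in the CUAL model, and no reason is given for using the yes/no form.

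When SAP 5.4.2.2 justifies the time offset, it states that "the CUAL count is expected to be mainly driven by new T2 lesions".

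The imputation analyses keep the same set: "the analysis is adjusted for the same covariates as for the main analysis" (9.7.2.3.1). The per-protocol and EOT + 7 days analyses also repeat the main adjustment.

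CUAL is in the fallback procedure of 9.1.1. It is tested with a two-sided Wald test at one third of 5%, or at two thirds if fatigue succeeds.

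**The concern.** Baseline lesion load can be expected to predict new lesions. If it does, reducing the Gd+ count to a flag and omitting T2 load leaves explainable between-subject variation in the dispersion parameter, and that widens the standard error of the rate ratio. The SAP's own reasoning sharpens the point: it expects T2 lesions to drive the endpoint but adjusts for no baseline T2 measure. For fatigue (9.7.1.2), by contrast, the baseline score stays continuous.

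The test is confirmatory at a reduced level, and its result decides how much alpha passes to 12-week CDA and then 24-week CDA (Table 8). The same covariates enter the CUAL imputation. There, subjects without a post-baseline scan are imputed from treatment and baseline covariates alone (10.1.1).

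**Working it through.** The SAP gives no CUAL rate, dispersion, rate ratio or power, so there is no figure to reproduce. The size can only be explored under stated assumptions.

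**From the SAP**
- "1133 subjects are randomized in two groups: ponesimod 20 mg or teriflunomide 14 mg, using a 1:1 ratio", so about 566.5 per arm.
- Local two-sided alpha: 0.05/3 = 0.0167, or 2 × 0.05/3 = 0.0333, which agrees with Table 8.

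**Assumed, not in the SAP**
- 4 CUALs per teriflunomide subject over the study; rate ratio 0.8.
- Residual dispersion k of 1 or 2; about 41% of subjects Gd+.
- Log T2 volume standardised and correlated with Gd+ activity.
- Prognostic slopes as in the table.

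**Analytic approximation.** Var(log RR) = Σ over arms of (1/μ + k)/n. With μ = 4 and 3.2 and k = 1: (1.25 + 1.3125)/566.5 = 0.00452, so SE = 0.067. The simulation without prognostic effects gives 0.0675, so the two agree.

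**Simulation.** 150 trials per scenario. The planned form uses the Gd+ flag only. The extended form uses the flag plus log(1 + Gd+ count) plus log T2 volume. Both strata and varying follow-up were left out of both forms. Equivalent N = 1133 / variance ratio.

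| Slopes (per log(1 + count); per SD of log T2 volume) | k | SE planned | SE extended | Variance ratio | Equivalent N |
|---|---|---|---|---|---|
| None (0; 0) | 1 | 0.0675 | 0.0675 | 1.001 | 1132 |
| None (0; 0) | 2 | 0.0897 | 0.0899 | 1.002 | 1131 |
| Count only (0.3; 0) | 1 | 0.0677 | 0.0675 | 0.995 | 1139 |
| Count only (0.3; 0) | 2 | 0.0899 | 0.0898 | 0.998 | 1135 |
| Weak (0.3; 0.2) | 1 | 0.0689 | 0.0677 | 0.962 | 1178 |
| Weak (0.3; 0.2) | 2 | 0.0912 | 0.0903 | 0.977 | 1160 |
| Moderate (0.5; 0.3) | 1 | 0.0722 | 0.0688 | 0.908 | 1248 |
| Moderate (0.5; 0.3) | 2 | 0.0935 | 0.0910 | 0.946 | 1198 |
| Strong (0.7; 0.5) | 1 | 0.0788 | 0.0708 | 0.805 | 1407 |
| Strong (0.7; 0.5) | 2 | 0.0997 | 0.0930 | 0.868 | 1305 |

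The ratios are model-based. The empirical ratio in the strong scenarios was lower still (about 0.5), but with 150 trials and a skewed covariate it is not relied on.

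**What this means for power.** Power = Φ(|ln RR|/SE − z). Take the moderate case with k = 1 at alpha 0.0167, so z = 2.394 and |ln 0.8| = 0.2231:
- planned: 0.2231/0.0722 − 2.394 = 0.70, power about 76%
- extended: 0.2231/0.0688 − 2.394 = 0.85, power about 80%

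**Where the gain comes from.** With a modest count effect alone the gain is under 1%. Most of it appears once T2 volume is prognostic.

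**Add or replace?** A separate simulation replaced the flag by log(1 + count) and added T2 volume. It assumed 1133 subjects, 45% Gd+, rate ratio 0.7 and 80 trials per scenario, with the Gd+ effect carried by presence. The variance ratios against the planned model were 1.03, 1.00, 1.06 and 1.08. Replacement can therefore cost up to about 8%. Keeping the flag and adding to it cost at most about 0.2%.

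**The case against.** The planned model is fully specified, is repeated consistently across the supportive analyses and matches the Gd+ subgroup coding in section 8. It leaves type I error untouched. On this view, choosing one baseline MRI covariate over another is a modelling preference. All of this stands against calling the model wrong; it does not show that there is no precision to gain.

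The flag also has a practical merit. Under 5.4.2.2.1 the baseline MRI counts as missing exactly when Gd+ presence is missing, so the flag drops no evaluable subject. T2 volume could be missing on its own, and its log is undefined at zero. Both need a written rule.

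Three stronger readings are tempting but not supported:

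- **That Gd+ status is the only adjustment.** The EDSS and DMT strata are in the model too; Gd+ status is the only MRI covariate.
- **That the gain is large and certain.** With rate ratio 0.5, residual dispersion 0.7-0.9 and slopes of 0.4-0.8 for the count and 0.2-0.4 for T2 volume, simulated SE ratios are 0.967, 0.921 and 0.854. That is 1/ratio² = 1.07, 1.18 and 1.37 times the information. Those inputs are chosen, not taken from the SAP, and they exclude the case of no gain.
- **That imputed counts are shown to be less precise.** This was not computed. Under 10.1.1, imputation conditions on each subject's observed counts, so only subjects without a post-baseline scan depend on baseline covariates alone, and this is a sensitivity analysis.

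**Conclusion.** The concern holds as a point of efficiency. The alpha-controlled CUAL model is valid, but it leaves out two centrally read baseline variables, one of them the measure closest to what the SAP says drives the endpoint. The variance of the log rate ratio would fall by 0% if they are not prognostic, about 2-9% for weak to moderate effects and up to about 20% for strong ones. These figures rest on assumed rates, dispersion, Gd+ prevalence and slopes; the SAP supplies none of them. Because adding the variables risks almost nothing under these assumptions, the change is worth making although the gain is uncertain.

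**What to change.** Before unblinding, amend 9.7.2.2 as follows:

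- Keep Gd+ T1 lesions absent/present, and **add** log(1 + baseline Gd+ T1 lesion count) and log(baseline T2 lesion volume + a small constant stated in the SAP).
- Set a missing T2 volume to the overall mean of all subjects, so that nobody is dropped.
- Use the same covariates in the imputation analyses of 9.7.2.3.1. The per-protocol and EOT + 7 days analyses follow automatically.
- Report the current model as a supportive analysis.

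The cost is two more model parameters, one missing-value rule and, if the protocol names the CUAL covariates, an entry in section 4.1. No new data are needed. If unblinding has already taken place, the extended model can serve only as a sensitivity analysis.
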